3.3. Invitation

3.3.1. Invitation methods

We will use NHS DigiTrials as the primary route for postal invitation with the intention to reach most of the U.K.'s adult population through our invitations. NHS DigiTrials provides unparalleled scale, the ability to target invitations based on demographic information, and will help us build trust with potential participants. The NHS DigiTrials application process includes Section 251 support which will enable NHS DigiTrials – on our behalf – to select eligible individuals and send named invitations for participation in Our Future Health. We will dynamically adjust the number of

invites sent to specific population groups based on conversion rates and our ambition to recruit a diverse cohort that is reflective of the UK population.

Invitations may also be sent by collaborations with community pharmacy networks using their existing customer databases. We are also exploring other ways to send invitations, including potential partnerships with existing cohorts such as REACT.

In partnership with NHS bodies, invitations to Our Future Health will be sent by email to blood donors by NHSBT, and through existing patient communication systems – which may include post, email and text message – in primary and secondary care. Text messages are attractive because they are inexpensive, already sent in high volume by the NHS, and can include a link to our participant information sheet and consent process that can be accessed via a patient’s smartphone or computer prior to a planned appointment. Our Public Advisory Board members and secondary care PPIE work in 2021 revealed that this was an acceptable and viable format, but with the caveat that it needs to come from a known and trusted source.

NHS primary and secondary care settings offer the opportunity to recruit a diverse cross-section of the UK population in terms of age, ethnicity and deprivation, countering concerns of the healthier, less diverse population that can typically be recruited from the blood donor population. For example, NHS primary care conducts the Health Check programme⁴⁹, which is offered every 5-years via postal invite to GP registrants aged 40 to 74 years. The Health Check programme has consistently higher uptake within higher deprived populations as well as within underrepresented ethnicities in health research including Indian, Caribbean and Chinese.⁵⁰

3.3.2. Feasibility of invitation strategy

The invitation methods described above have high feasibility based on past use of the infrastructure by prior studies.

The largest UK example of a successful postal recruitment strategy is UK Biobank. Individuals registered with the NHS were invited by post and able to respond via post, internet, or phone to arrange an appointment at an assessment centre. Consent, questionnaire, baseline measurements, and phlebotomy were all conducted at assessment centres that were specially designed and fitted out for this purpose.

NHS DigiTrials is a similar, more formalised process to invite NHS-registered individuals to research studies, which is already demonstrating success with recruitment to the Randomised Evaluation of COVID-19 Therapy (RECOVERY) trial and the Platform Randomised trial of Interventions against COVID-19 In older people (PRINCIPLE) Trial.⁵¹

We have already demonstrated the feasibility of NHSBT email invitations sent to blood donors in joining Our Future Health and this pilot study is summarised in **Appendix D**. In addition, INTERVAL⁵² and COMPARE⁵³ studies have already successfully demonstrated recruitment of blood

⁴⁹ <https://www.nhs.uk/conditions/nhs-health-check/>

⁵⁰ Cook et al (*Int J Equity Health*, 2016) Who uses NHS health checks? Investigating the impact of ethnicity and gender and method of invitation on uptake of NHS health checks. <https://pubmed.ncbi.nlm.nih.gov/26791963/>

⁵¹ <https://digital.nhs.uk/features/nhs-digitrials-already-saving-lives>

⁵² <https://www.intervalstudy.org.uk/>

⁵³ <https://www.comparestudy.org.uk/>

donors for research studies that use the first 35 ml of blood that would otherwise be discarded for infection control, while the STRategies to Improve Donor ExperienceS (STRIDES) study⁵⁴ is also currently successfully recruiting blood donors.

With regards to NHS primary and secondary care, we are conducting discovery work to establish optimal ways in which to recruit from existing hospital outpatient lists, while Born in Bradford⁵⁵ successfully recruited participants in NHS GP practices. Our work to date has included PPIE work comprising a series of multi-disciplinary consultations with patients, public, health care professionals and healthcare research delivery teams to understand how Our Future Health would be received and adopted alongside existing research portfolios. We have also had discussions with Genes and Health to identify commonalities in recruitment strategies and optimise invitations to attract a wider cohort of participants.

3.3.3. Invitation development

We will take a theory- and evidence-based approach to the development of our invitation content. Specifically, we will conduct user research to assess comprehension and acceptability of invitations and use randomised online experiments to identify content that maximises response.

For digital invitations, where possible, we will send a limited number of pre-invitation notifications and invite reminders to optimise response rates. This has been validated in the findings from our PPIE work in primary and secondary care and via input from our Public Advisory Board.

To avoid excluding individuals who do not own a smartphone or have lower digital literacy, in addition to postal invites, we will develop the ability to enable hardcopy and telephone completion of the consent form and questionnaires.

3.4. Reimbursement

Our Future Health is committed to the principle of equity in participation and widening access as substantially as possible. One such initiative is offering reimbursement to compensate for the time and costs incurred to participate in Our Future Health. We intend reimbursement to reduce practical barriers to participation, increasing response rates in those who may otherwise be less likely to participate.

Participants joining Our Future Health through via the community route will be offered reimbursement in the form of a £10 voucher once they have completed all the steps to becoming a full participant. In order to be eligible for reimbursement, participants must register, consent, attend a clinic appointment to donate a blood sample, and complete an on-line questionnaire. Once eligible, participants will be required to claim the £10 voucher within a set period, and to then digitally redeem this voucher from the provider within 28 days.

⁵⁴ <https://www.strides-study.org.uk/>

⁵⁵ <https://borninbradford.nhs.uk/>

3.5. Consent

The primary method of consent in Our Future Health will be digital. The consent process starts with information provision which comprises the consent form and the participant information sheet, opportunities for potential participants to have their questions answered, and a formal recording that the individual consents to participate in the Our Future Health research programme. Participants register an account with their contact details either before or at the time of consent so we know who the consent belongs to, and so we can contact that person as part of their involvement in the programme.

We designed the consent and participant information sheet in alignment with the principles set out in our Ethics & Governance Framework, namely that valid consent comprises three components: information, comprehension, and voluntariness. For further details, please see the Ethics & Governance Framework (**Appendix B**).

The consent form and participant information sheet were rigorously co-developed with members of the public in the following forums:

- 18 focus groups with 82 members of the public.
- 4 meetings with a co-design group comprised of 8 members of the public (a different group to the two that informed the design of the leaflet and video scripts).
- 21 user testing interviews with members of the public (who had previously participated in one of the 18 focus groups).

We worked with Claremont and digital agency Kainos on three rounds of user testing (total n=36) of the participant information sheet (along with other parts of the digitally-delivered process including registration form, consent form, and questionnaire completion). We also had input to the first version of the participant information sheet from the Ethics & Feedback Advisory Group as well as other external stakeholders and advisers including national and international experts in consent from academia. The consent form and participant information sheet were approved by the REC and used in the pilots studies. We recently revised these forms again, after feedback from our participants and with consultation and re-review by our governance Boards, including the Public Advisory Board and the Ethics Advisory Board. We also conducted individual user testing interviews with nine members of the public.

The consent includes the ability to recontact participants, so we can invite them to complete additional questionnaires, provide further samples, receive personal health-related information, and consider invitations to enrol in future (stage 2) studies that will have separate REC-approved study protocols with their own consents and participant information sheets. Some stage 2 studies may recruit participants based on their risk of specific diseases calculated from their self-reported, genetic and/or other health-related information.

We will continue to use our Participant-Reported Experiences Survey (**Appendix C**), which over 900 participants have completed to date, to obtain feedback on the ease and acceptability of the consent process, and as part of our evaluation/analytics and insights.

Individuals with queries can call or email the Our Future Health support centre, which will expand in capacity as our recruitment scales. The support centre will be operated by specially trained staff using an integrated computer system developed for, and dedicated to, Our Future Health. The main functions of the support centre are to:

- Answer questions about consent procedures and the scope of Our Future Health
- Allow questions from potential participants (and their GPs) to be addressed either by the trained call centre staff or, if not possible, by more senior members of the Our Future Health team
- Administer the questionnaire to visually impaired participants, and those who do not or cannot access the questionnaire via the website/digitally

Continued interactions with our participants and the public through the Participant-Reported Experiences Survey and the support centre, respectively, will ensure we can iterate the consent and participant information sheet further, if required, with updates sent to the REC for review and approval prior to deployment.

3.5.1. Participants without capacity to consent

After a participant has consented to be part of Our Future Health, they may subsequently lose capacity (e.g. due to dementia). In such situations we need to balance the ethical requirements to enable access to research participation, as well as protecting vulnerable participants from intrusive or interventional research.

There are two situations where we may become alert to potential changes in capacity:

1. Directly contacted by a representative of the participant
2. From our regular updating of the health information through linkage with national data controllers

For option 1, we will establish a process where we verify the identity of the participant and the legal status of the reporting individual. Once verified we will proceed to our loss of capacity process detailed below.

Option 2 is complex since there are no codes in the medical record which indicate loss of capacity either temporarily or permanently. There are some medical conditions in which loss of capacity is more common and these include: strokes, dementias, and traumatic brain injury. Using only diagnosis codes can be misleading since this is not the same as loss of capacity. Studies have reported that individuals diagnosed with stroke, mild-moderate dementia, and traumatic brain injury results in a 2%⁵⁶, 26%⁵⁷ and 47%⁵⁸ likelihood, respectively, of lacking capacity to consent within a year of diagnosis.

We do not yet know if it is possible to develop an algorithm that can accurately predict who has lost capacity using clinical codes due to the following points:

1. Discovery and validation of an algorithm requires formal assessments of capacity in identified participants.

⁵⁶ Pendlebury ST. Stroke-related dementia: Rates, risk factors and implications for future research. *Maturitas*. 2009;64(3):165-71.

⁵⁷ Guarino PD, Vertrees JE, Asthana S, Sano M, Llorente MD, Pallaki M, et al. Measuring informed consent capacity in an Alzheimer's disease clinical trial. *Alzheimers Dement (N Y)*. 2016;2(4):258-66.

⁵⁸ Thornhill S, Teasdale GM, Murray GD, McEwen J, Roy CW, Penny KI. Disability in young people and adults one year after head injury: prospective cohort study. *BMJ*. 2000;320(7250):1631-5.

2. Capacity is a temporal and decision-specific assessment with considerable heterogeneity between patients with the same diagnosis, which increases the risk of any algorithm of inappropriately excluding individuals from research.

We therefore propose that, once we have obtained linked healthcare data, we collaborate with other research programmes to propose a research study to develop a loss of capacity algorithm. This algorithm would be based on broad clinical codes (ICD, Read, SNOMED) and would require formal capacity assessments to be conducted. If a validated algorithm with high positive predictive value and sensitivity in identifying individuals who have lost capacity can be developed, we will explore the appropriateness of using it to identify participants who should proceed through our loss of capacity process. This will require careful interpretation of the Mental Capacity Act, and engagement with participant representatives.

3.6. Baseline questionnaire

We have developed a baseline questionnaire to capture health and lifestyle factors that would be difficult or impossible to obtain from data linkages. This questionnaire was developed largely by a core scientific advisory team and was intended to align closely to existing large epidemiological cohorts, such as the UK Biobank. We went through a process of cognitive testing with Our Future Health participants to refine how questions are asked and understood. The baseline questionnaire collects information on demographics, socioeconomics, physical activity, lifestyle exposures, family history, medical history, depression and anxiety, medications, and supplements. It takes, on average, 35 minutes to complete. This initial version of the baseline questionnaire was previously approved by the REC and was used in pilots conducted in 2021, in which we collected complete questionnaire data on over 1,500 people (report of pilots attached as **Appendix D**).

Piloting, additional cognitive testing, and internal scientific review has enabled us to identify and design improvements to the baseline questionnaire as well as expand slightly on health and family history sections. The changes have been reviewed by the Scientific Advisory Board and are included in **Appendix E**.

From our pilot studies, we know that 95% of participants who start the baseline questionnaire complete it. During early phase recruitment, we will test whether deploying the questionnaire before or after phlebotomy has significant effects on attaining full recruitment of an individual, defined as provision of consent, completion of the baseline questionnaire, and donation of a blood sample.

3.7. Short baseline questionnaire

We will develop a short version of the questionnaire. This will be a shortened list of the already-approved questions from our baseline questionnaire. There will be no additional items or new question types.

The items that comprise the short questionnaire will be selected by:

1. Data reduction approaches
Where several items have been included to measure the same underlying phenotype, we will identify cardinal items for inclusion in short questionnaire using data reduction approaches.

We will use pilot data to examine the internal validity (Cronbach alpha) of any related items. We will establish inter-item correlations and perform factor analyses to establish the overall fit, factor scores and item loadings. We will iteratively drop less well performing items and re-evaluate internal validity using Cronbach alpha and factor analyses until we find the minimum number of items that can be used to index the underlying outcome.

2. Stakeholder input

We will review the results from this data driven approach with stakeholders including our scientific advisory board and participant advisory board. We will collect input from stakeholders on priorities for retention and outcomes or items that do not represent immediate priorities for healthcare research.

3. Testing and piloting

We will pilot the resultant shorter questionnaire with members of the public to establish whether the time taken to complete meets our length criteria (<10minutes) and to ensure it is being understood and is generally acceptable to participants.

When we have a satisfactory short questionnaire, we will test it against the longer baseline questionnaire to establish whether rates of conversion to full participant (consent + blood sample + questionnaire) are improved. The short form questionnaire may enable a streamlined, in-person, full participant recruitment model to be deployed in the field, if desired or required. Any participants who complete a short core questionnaire will be asked to provide responses to the remaining questions from the primary baseline questionnaire after recruitment.

3.8. Phlebotomy and physical measurements

We will record physical measurements and collect a blood sample from each consented participant at an in-person appointment in one of the following settings:

1. Community covering pharmacies, mobile units, and 'pop-up' clinics
2. Existing NHSBT appointments for blood donations
3. Existing NHS appointments for health care phlebotomy

Participants will have a choice in where they donate their blood and undergo a brief physical assessment. Location choice will largely be within the community route (pharmacy collaborations, Our Future Health mobile units and 'pop-up' clinics). If the participant has been recruited through an NHS route, then they will likely automatically be in an existing phlebotomy route such as blood donation, or primary or secondary health care.

As general practice, two vials of blood will be drawn from participants. However, up to five vials of blood could be taken for purposes such as quality control or where samples may be unusable. Blood samples will be used to extract DNA and conduct genotyping, as well as conduct baseline assessments of cholesterol and HbA1c and will be sent to our biobank for long-term storage. At all opportunities the blood collection time and date, and time of last significant meal will be collected at the time of blood draw. Physical measurements will also be taken at this time including blood pressure, height, weight, and waist circumference.

Point of care testing (POCT) for cholesterol will also be offered to participants at their clinic appointment. The cholesterol test will be performed using a finger-prick blood test with the Mission POCT device, which is approved for use by the NHS. Whilst all participants will have the

option of receiving the results of their POCT on a proforma, alongside other physical measurements taken at the appointment, these measurements are taken for research purposes only –not clinical or diagnostic purposes and are not a personal health check/substitute for the NHS Health Check.

Advice to participants about their cholesterol reading will be explained in the proforma given to them at the clinic appointment, with their result recorded. For participants who receive a cholesterol reading greater than 9 in the first test (or greater than 7.5 if under the age of 30), a repeat test using the same device will be performed. Participants will only be directed to inform their GP if the measurement of their total cholesterol (after a repeat test in the same appointment) is greater than 9.0 (and they are over 30) or greater than 7.5 (and they are under 30), to enable further work-up for a possible diagnosis of familial hypercholesterolaemia unless any of the following apply:

- They have had an NHS Health Check in the last 5 years.
- They are having yearly checks for heart disease, stroke or diabetes.
- They remember having their cholesterol measured in the last 2 years.

In each of the above cases, participants will be informed that there is no need to inform their GP, regardless of their measurement.

Participants will also be directed to visit the following page on the British Heart Foundation website: [bhf.org.uk/informationsupport/risk-factors/high-cholesterol](https://www.bhf.org.uk/informationsupport/risk-factors/high-cholesterol), in order to learn more about cholesterol levels and how these can be reduced through lifestyle changes.

[figure not shown]

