6.4. Examples of participant feedback

Below are some examples of the types of feedback that are being considered:

- (a) Questionnaire insights are under development and may include comparisons to healthy recommendations, comparisons to the population, as well as resources participants may wish to consult.
- (b) Baseline physical measurements (blood pressure, height, weight, waist circumference) as well as baseline blood measures of cholesterol. These measurements are not intended to be a 'health check' and are not, for now, shared with their GP or the NHS. However, we are working with the NHS and the Office for Health Improvement and Disparities to explore potential options for sharing these data with the NHS in the future. We will provide written feedback to participants about their blood pressure, heart rate, and cholesterol (from a POCT/ 'finger-prick' test) on a proforma with advice to contact NHS 111, a Pharmacist or GP in the rare circumstances where that is necessary or if they have e(i.e measurements that warrant medical attention immediately or within days e.g. a very low heart rate). For the vast majority of results, we will also direct participants to the NHS website on blood pressure, and the British Heart Foundation website on cholesterol where they can obtain further information and advice.
- (c) Being approached by NHSBT if their genotypes suggest that they have less common minor blood group antigens that are underrepresented among NHSBT blood donors. This may be particularly beneficial for minority groups for whom NHSBT sometimes has difficulty providing optimally matched blood products.
- (d) Providing participants with increased access to information stored in their NHS health care records.
- (e) Integrated risk scores that provide disease risk estimates. Leading integrated risk score candidates that may initially be feedback to participants include cardiovascular disease,⁶² age-related macular degeneration, glaucoma, and type II diabetes. Each of these integrated risk scores provides good risk prediction and are clinically actionable.
- (f) Other examples include risk predictions based on common genetic variants associated with risk of iron overload, deep venous thrombosis, or that influence the efficacy or side effects of prescription drugs.

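### The rule in section 3.8 for directing participants to their GP about cholesterol has no branch for age 30, although the repeat-test rule just before it does

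*Protocol*

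**What the plan says.** Section 3.8 (Phlebotomy and physical measurements) sets out the optional point-of-care cholesterol test and what follows a high reading. Two consecutive sentences carry the decision rules.

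- **Repeat test.** A second test on the same device is done if the reading is "greater than 9 in the first test (or greater than 7.5 if under the age of 30").
- **Direction to the GP.** "Participants will only be directed to inform their GP if the measurement of their total cholesterol", after the repeat, is "greater than 9.0 (and they are over 30) or greater than 7.5 (and they are under 30"). The stated purpose is work-up for possible familial hypercholesterolaemia. Three exemptions follow: a recent NHS Health Check, yearly checks for certain conditions, or a remembered recent cholesterol measurement.

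On how this reaches the participant, the section says: "Advice to participants about their cholesterol reading will be explained in the proforma given to them at the clinic appointment". It also points everyone to further reading: "Participants will also be directed to visit the following page on the British Heart Foundation website". It states that "these measurements are taken for research purposes only".

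Section 6.4(b) describes written feedback "on a proforma with advice to contact NHS 111, a Pharmacist or GP in the rare circumstances where that is necessary". It gives no cholesterol threshold and no age boundary.

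**The concern.** The two rules use the same pair of thresholds but cut age differently. The repeat-test rule names only the younger group and puts everyone else on the limit of 9, so age 30 is covered. The GP rule names both groups, one strictly above 30 and one strictly below. In completed years, which is how age is usually recorded and applied, age 30 belongs to neither.

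The word *only* in the GP rule makes its conditions exhaustive. A missing branch therefore means that the participant is not directed, rather than that staff may use their judgement. Taken literally, a participant aged 30 would be re-tested because of a reading above 9, confirmed above 9.0, and then not told to inform the GP.

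This is the only sentence in the protocol that states the cholesterol reading at which a participant is told to inform the GP, so its age boundary should be unambiguous. Nor is the NHS Health Check a routine backstop at that age: section 3.3.1 says it is offered to people aged 40 to 74.

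**Working it through.** The protocol has no figure to reproduce here. The check is a logical comparison of the two rules.

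**Inputs**, all from section 3.8 unless stated. Write *a* for age in completed years and *c* for the reading.

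- Repeat test: *c* > 7.5 if *a* < 30, otherwise *c* > 9.
- GP direction as written: (*c* > 9.0 and *a* > 30) or (*c* > 7.5 and *a* < 30).
- GP direction as proposed: (*c* > 9.0 and *a* ≥ 30) or (*c* > 7.5 and *a* < 30).
- Ages 18 to 100, which is 100 − 18 + 1 = 83 completed ages. The lower end is the lowest age in Table 1; the upper end is arbitrary and does not affect the result.

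The exemptions are left out of the comparison because none of them depends on being 30.

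**Around the boundary**

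| Age | Reading | Repeat test | GP as written | GP as proposed |
|---|---|---|---|---|
| 29 | 7.6 | yes | yes | yes |
| 29 | 9.1 | yes | yes | yes |
| 30 | 9.0 | no | no | no |
| 30 | 9.1 | yes | **no** | yes |
| 31 | 9.0 | no | no | no |
| 31 | 9.1 | yes | yes | yes |

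**Over all 83 ages**

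| Reading | Ages re-tested | Ages directed, as written | Mismatch |
|---|---|---|---|
| 7.6, 8.0, 9.0 | 12 (ages 18 to 29) | 12 | none |
| 9.1, 10, 12 | 83 | 82 | age 30 |

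With *30 or over* in place of *over 30*, the two rules agree at every age and reading tested.

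**Alternative reading.** If *over 30* means any time after the 30th birthday, only the birthday itself falls outside both branches: 1/365.25 = 0.27% of that year of age.

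**Scale.** Table 1 gives the following for ages 30 to 39: 347,493 + 17,760 + 44,405 + 12,902 + 343,187 + 15,893 + 44,993 + 14,818 = 841,451. Assuming an even spread over the ten years, about 841,451/10 ≈ 84,000 of the full 5 million (1.7%) would be aged 30. That is not a count of people affected. It would have to be multiplied by the share who accept the finger-prick test, the share whose repeated reading exceeds 9.0, and the share who meet none of the three exemptions. The protocol gives none of these, so no number affected can be derived.

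**Whether other text closes the gap.** Section 6.4(b) describes general advice to seek help but sets no limit, so it does not say what happens at age 30. The stated purpose of the GP direction gives no reason to leave that age out.

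**The case against.** The strongest answer is that the text corrects itself. The repeat-test rule immediately before shows where the cut was meant to fall, nobody would re-test a 30-year-old above 9 with the aim of then saying nothing, and a sensible reader would apply the intended rule. On that view this is loose drafting and no more. The gap also depends on reading age in completed years; on the other reading it is a single day. The form that staff and participants would actually use is the proforma, which is not among the documents, so no effect in clinic has been shown. The consequence is limited as well: the participant can still have the result, is pointed to the British Heart Foundation page, may fall under the general advice in section 6.4(b), and is told that the measurements are for research.

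All of this is fair, and it sets the importance of the point. It does not remove the inconsistency. Relying on the reader to infer the rule concedes that the sentence, followed literally, gives the wrong answer at age 30. The sentence tells staff what to do after a very high reading; it is not background text. The age counts above only locate the mismatch. They measure neither people nor risk.

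**Conclusion.** The point holds, at low severity. In completed years the GP-direction rule omits age 30 and so contradicts the repeat-test rule beside it. The mismatch is confined to one year of age and to readings above 9.0; on the past-the-birthday reading it shrinks to one day. That *30 or over* was meant is an inference from the neighbouring rule, but a very safe one. The number of people affected cannot be estimated from the protocol, and no effect in the clinic is claimed because the proforma has not been seen. Sample size, recruitment, data collection and analysis are untouched.

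**What to change.** In section 3.8, replace *over 30* with *30 or over* in the GP-direction sentence, so that its age boundary matches that of the repeat-test sentence. Check that the participant proforma uses the same boundary and correct it if it repeats the present phrase. The cost is one wording change in the protocol and possibly one in the proforma. No threshold, exemption or procedure changes.
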